6.5. Diet/Activity/Other Considerations

6.5.1. Diet

Subjects should maintain a normal diet unless modifications are required to manage an AE such as diarrhea, nausea or vomiting.

6.5.2. Contraception

Pembrolizumab may have adverse effects on a fetus in utero. Furthermore, it is not known if pembrolizumab has transient adverse effects on the composition of sperm. For this trial, male subjects will be considered to be of non-reproductive potential if they have azoospermia (whether due to having had a vasectomy or due to an underlying medical condition).

Female subjects will be considered of non-reproductive potential if they are either:

(1) postmenopausal (defined as at least 12 months with no menses without an alternative medical cause; in women < 45 years of age a high follicle stimulating hormone (FSH) level in the postmenopausal range may be used to confirm a post-menopausal state in women not using hormonal contraception or hormonal replacement therapy. In the absence of 12 months of amenorrhea, a single FSH measurement is insufficient.);

OR

(2) have had a hysterectomy and/or bilateral oophorectomy, bilateral salpingectomy or bilateral tubal ligation/occlusion, at least 6 weeks prior to screening;

OR

(3) has a congenital or acquired condition that prevents childbearing.

Female and male subjects of reproductive potential must agree to avoid becoming pregnant or impregnating a partner, respectively, while receiving study drug and for 120 days after the last dose of study drug by complying with one of the following: (1) practice abstinence[†] from heterosexual activity;

OR

(2) use (or have their partner use) acceptable contraception during heterosexual activity.

Acceptable methods of contraception are[‡]:

Single method (one of the following is acceptable):

- intrauterine device (IUD)
- vasectomy of a female subject's male partner
- contraceptive rod implanted into the skin

Combination method (requires use of two of the following):

- diaphragm with spermicide (cannot be used in conjunction with cervical cap/spermicide)
- cervical cap with spermicide (nulliparous women only)
- contraceptive sponge (nulliparous women only)
- male condom or female condom (cannot be used together)
- hormonal contraceptive: oral contraceptive pill (estrogen/progestin pill or progestinonly pill), contraceptive skin patch, vaginal contraceptive ring, or subcutaneous contraceptive injection

[†]Abstinence (relative to heterosexual activity) can be used as the sole method of contraception if it is consistently employed as the subject's preferred and usual lifestyle and if considered acceptable by local regulatory agencies and ERCs/IRBs. Periodic abstinence (e.g., calendar, ovulation, sympto-thermal, post-ovulation methods, etc.) and withdrawal are not acceptable methods of contraception.

‡If a contraceptive method listed above is restricted by local regulations/guidelines, then it does not qualify as an acceptable method of contraception for subjects participating at sites in this country/region.

Subjects should be informed that taking the study medication may involve unknown risks to the fetus (unborn baby) if pregnancy were to occur during the study. In order to participate in the study subjects of childbearing potential must adhere to the contraception requirement (described above) from the day of study medication initiation (or 14 days prior to the initiation of study medication for oral contraception) throughout the study period up to 120 days after the last dose of trial therapy. If there is any question that a subject of childbearing potential will not reliably comply with the requirements for contraception, that subject should not be entered into the study.

6.5.3. Use in Pregnancy

If a subject inadvertently becomes pregnant while on treatment with pembrolizumab, the subject will immediately be removed from the study. The site will contact the subject at least monthly and document the subject's status until the pregnancy has been completed or terminated. The outcome of the pregnancy will be reported to Merck without delay and within 2 working days to Merck if the outcome is a serious adverse experience (e.g., death, abortion, congenital anomaly, or other disabling or life-threatening complication to the mother or newborn).

The study investigator will make every effort to obtain permission to follow the outcome of the pregnancy and report the condition of the fetus or newborn to Merck. If a male subject impregnates his female partner the study personnel at the site must be informed immediately and the pregnancy reported to Merck and followed as described above and in section 9.2.

6.5.4. Use in Nursing Women

It is unknown whether pembrolizumab is excreted in human milk. Since many drugs are excreted in human milk, and because of the potential for serious adverse reactions in the nursing infant, subjects who are breast-feeding are not eligible for enrollment.

6.6. Participant Withdrawal/Discontinuation Criteria

Participants may withdraw consent at any time for any reason or be dropped from the trial at the discretion of the investigator should any untoward effect occur. In addition, a participant may be withdrawn by the investigator if enrollment into the trial is inappropriate, the trial plan is violated, or for administrative and/or other safety reasons. Specific details regarding discontinuation or withdrawal are provided in section 8.4 – Other Procedures.

A participant must be discontinued from the trial for any of the following reasons:

- The subject or legal representative (such as a parent or legal guardian) withdraws consent.
- Disease progression (for definition see Section12)
- Unacceptable adverse experiences as described in Section 7.0
- Intercurrent illness that prevents further administration of treatment
- Investigator's decision to withdraw the subject
- The participant has a confirmed positive serum pregnancy test
- Noncompliance with trial treatment or procedure requirements
- The subject is lost to follow-up
- Completed 35 cycles of treatment with pembrolizumab

Note: Subjects who stop pembrolizumab after 35 cycles may be eligible for up to 18 cycles of additional study treatment if they progress after stopping study treatment provided they meet the requirements detailed in Section8.5.4.

• Administrative reasons

The End of Treatment and Follow-up visit procedures are listed in Section 10 (Study calendar) and Section 8.5 (Visit Requirements). After the end of treatment, each subject will be followed for 120 days for adverse event monitoring (events of clinical interest will be collected for 120 days after the end of treatment). Subjects who discontinue for reasons other than progressive disease will have post-treatment follow-up for disease status until disease progression, initiating a non-study cancer treatment, withdrawing consent or becoming lost to follow-up. After documented disease progression each subject will be followed by telephone for overall survival until death, withdrawal of consent, or the end of the study, whichever occurs first.

6.7. Discontinuation of Study Therapy after CR

Discontinuation of treatment may be considered for subjects who have attained a confirmed CR that have been treated for at least 24 weeks with pembrolizumab and had at least two

treatments with pembrolizumab beyond the date when the initial CR was declared. Subjects who then experience radiographic disease progression may be eligible for up to 18 cycles of additional treatment with pembrolizumab via the Second Course Phase at the discretion of the investigator if no cancer treatment was administered since the last dose of pembrolizumab, the subject meets the safety parameters listed in the Inclusion/Exclusion criteria, and the trial is open. Subjects will resume therapy at the same dose and schedule at the time of initial discontinuation. Additional details are provided in Section 8.5.

6.8. Treatment beyond Disease Progression

Immunotherapeutic agents such as pembrolizumab (MK-3475) may produce antitumor effects by reactivating endogenous cancer-specific immune responses, which may be functionally exhausted. The response patterns seen with such therapies may extend beyond the typical time course of responses seen with cytotoxic agents, and can manifest a clinical response after an initial increase in tumor burden or even the appearance of new lesions. Standard RECIST criteria may not provide an accurate or complete response assessment of immunotherapeutic agents such as pembrolizumab (MK-3475). Data from previous trials has clearly demonstrated a phenomenon in which patients treated with PD-1 inhibitors may derive clinical benefit despite initial radiologic evidence of disease progression[46]. Therefore, RECIST 1.1 will be used with the following adaptation: If radiologic imaging by local/site assessment shows PD, tumor assessment may be repeated > 4 weeks later in order to confirm PD with the option of continuing treatment per below while awaiting radiologic confirmation of progression. If repeat imaging shows SD, PR or CR, treatment may be continued as per treatment calendar. If repeat imaging still meets the threshold for PD (> 20% increase in tumor burden compared to nadir) but shows a reduction in tumor burden compared to the previous time point, treatment may be continued as per treatment calendar after consultation with Sponsor Investigator. If repeat imaging confirms progressive disease without reduction in tumor burden compared to the previous time point, subjects will be discontinued from study therapy. In determining whether or not the tumor burden has increased or decreased, investigators should consider all target lesions as well as non-target lesions.

The decision to continue study treatment after the 1st evidence of disease progression is at the Investigator's discretion based on the clinical status of the subject as described in Section 8.5.5.

7.0 Dose Modifications

7.1. General Principles

Dose modifications will be made based only on the guidelines described in Section 7.0. Patients requiring treatment to be held > 42 days for recovery from toxicity must discontinue protocol treatment. Adverse events (both non-serious and serious) associated with Pembrolizumab exposure may represent an immunologic etiology. These adverse events may occur shortly after the first dose or several months after the last dose of treatment. Pembrolizumab must be withheld for drug-related toxicities and severe or life-threatening AEs as per Table 3 below. See Section 6.4 (Supportive Care Guidelines), Table 2 and

Appendix 17.3 for supportive care guidelines, including use of corticosteroids. For subjects whose dose interval was increased due to toxicity, subjects may resume Pembrolizumab upon resolution of toxicity to Grade 0-1 or baseline. This dose would be considered Day 1 of the next cycle and should be in alignment with the new schedule

Toxicity	Hold Treatment For Grade	Timing for Restarting Treatment	Discontinue Subject if
Diarrhea/Colitis	2-3	Toxicity resolves to Grade 0-1.	Toxicity does not resolve to grade 0-1 within 6 weeks of last dose or inability to reduce corticosteroid to 10 mg or less of prednisone or equivalent per day within 12 weeks.
	4	Permanently discontinue	Permanently discontinue
AST, ALT, or	2-3	Toxicity resolves to Grade 0-1	Toxicity does not resolve to grade 0-1 within 6 weeks of last dose.
Increased Bilirubin	4	Permanently discontinue	Permanently discontinue
Type 1 diabetes mellitus (if new onset) or Hyperglycemia	T1DM or 3-4	Hold Pembrolizumab for new onset Type 1 diabetes mellitus or Grade 3- 4 hyperglycemia associated with evidence of beta cell failure.	Resume Pembrolizumab when patients are clinically and metabolically stable.
Hypophysitis	2-3	Toxicity resolves to Grade 0-1	Toxicity does not resolve to grade 0-1 within 6 weeks of last dose or inability to reduce corticosteroid to 10 mg or less of prednisone or equivalent per day within 12 weeks.
	4	Permanently discontinue	Permanently discontinue
Hyperthyroidism	3	Toxicity resolves to Grade 0-1	Toxicity does not resolve to grade 0-1 within 6 weeks of last dose or inability to reduce corticosteroid to 10 mg or less of prednisone or equivalent per day within 12 weeks.
	4	Permanently discontinue	Permanently discontinue
Hypothyroidism		Therapy with Pembrolizumab can be continued while treatment for the thyroid disorder is instituted	Therapy with Pembrolizumab can be continued while treatment for the thyroid disorder is instituted.
Infusion Reaction	3-4	Permanently discontinue	Permanently discontinue

Table 3. Dose Modification Guidelines for Pembrolizumab-Related Adverse Events

Toxicity	Hold Treatment For Grade	Timing for Restarting Treatment	Discontinue Subject if	
Pneumonitis	2	Toxicity resolves to Grade 0-1	xicity resolves to Grade 0-1 Toxicity does not resolve to grade 0-1 within 6 weeks of last dose or inability to reduce corticosteroid to 10 mg or less of prednisone or equivalent per day within 12 weeks.	
	3-4	Permanently discontinue	Permanently discontinue	
Renal Failure or Nephritis	2	Toxicity resolves to Grade 0-1	-1 Toxicity does not resolveto grade 0-1 within 6 weeks of last dose -1 or inability to reduce corticosteroid to 10 mg or less of prednisone or equivalent per day within 12 weeks.	
	3-4	Permanently discontinue	Permanently discontinue	
All Other Drug- Related	3 or Severe	Toxicity resolves to Grade 0-1	Toxicity does not resolve to grade 0-1 within 6 weeks of last dose or inability to reduce corticosteroid to 10 mg or less of prednisone or equivalent per day within 12 weeks.	
Toxicity ^{1,2}	4	Permanently discontinue	Permanently discontinue	

Note: Permanently discontinue for persistent grade 2 or 3 adverse reactions (excluding endocrinopathies controlled with hormone

replacement therapy) that do not recover to Grade 0-1 within 6 weeks after last dose of Pembrolizumab

¹ Pembrolizumab-specific exclusions to grade 3 non-hematologic toxicity as DLT include:

- Grade 3 rash in the absence of desquamation, no mucosal involvement, does not require steroids, and resolves to Grade
 1 by the next scheduled dose of pembrolizumab.
- 2. Transient Grade 3 AST or ALT elevation, defined as no more than 3 days with or without steroid use

² Pembrolizumab-specific DLT: Episcleritis, uveitis, or iritis of Grade 2 or higher

Dosing interruptions are permitted in the case of medical / surgical events or logistical reasons not related to study therapy (e.g., elective surgery, unrelated medical events, patient vacation, and/or holidays). Subjects should be placed back on study therapy within 6 weeks of the scheduled interruption, unless otherwise discussed with the PI. The reason for interruption should be documented in the patient's study record.

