- For Grade 2 diarrhea/colitis that persists greater than 3 days, administer oral corticosteroids.
- For **Grade 3 or 4 diarrhea/colitis** that persists > 1 week, treat with intravenous steroids followed by high dose oral steroids.
- When symptoms improve to Grade 1 or less, steroid taper should be started and continued over no less than 4 weeks.

Type 1 diabetes mellitus (if new onset, including diabetic ketoacidosis [DKA]) or \geq Grade 3 Hyperglycemia, if associated with ketosis (ketonuria) or metabolic acidosis (DKA)

- Insulin replacement therapy is recommended for Type I diabetes mellitus and for Grade 3-4 hyperglycemia associated with metabolic acidosis or ketonuria.
- Evaluate patients with serum glucose and a metabolic panel, urine ketones, glycosylated hemoglobin, and C-peptide.

Hypophysitis:

- For **Grade 2** events, treat with corticosteroids. When symptoms improve to Grade 1 or less, steroid taper should be started and continued over no less than 4 weeks. Replacement of appropriate hormones may be required as the steroid dose is tapered.
- For **Grade 3-4** events, treat with an initial dose of IV corticosteroids followed by oral corticosteroids. When symptoms improve to Grade 1 or less, steroid taper should be started and continued over no less than 4 weeks. Replacement of appropriate hormones may be required as the steroid dose is tapered.

Hyperthyroidism or Hypothyroidism:

Thyroid disorders can occur at any time during treatment. Monitor patients for changes in thyroid function (at the start of treatment, periodically during treatment, and as indicated based on clinical evaluation) and for clinical signs and symptoms of thyroid disorders.

- Grade 2 hyperthyroidism events (and Grade 3-4 hypothyroidism):
 - \circ In hyperthyroidism, non-selective beta-blockers (e.g. propranolol) are suggested as initial therapy.
 - In hypothyroidism, thyroid hormone replacement therapy, with levothyroxine or liothyroinine, is indicated per standard of care.
- Grade 3-4 hyperthyroidism
 - Treat with an initial dose of IV corticosteroid followed by oral corticosteroids. When symptoms improve to Grade 1 or less, steroid taper should be started and continued over no less than 4 weeks. Replacement of appropriate hormones may be required as the steroid dose is tapered.

Hepatic:

- For **Grade 2** events, monitor liver function tests more frequently until returned to baseline values (consider weekly).
 - o Treat with IV or oral corticosteroids

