Adverse events will be assessed continuously throughout the study. If 6 of the first 12 patients have to discontinue study treatment due to treatment related adverse events the study will be interrupted for consideration of dose reduction or termination. If ever 8 of the 21 eligible patients have to discontinue study treatment due to treatment related adverse events the study will be suspended and early termination for excess toxicity will be considered after careful investigation of the causes of the higher than expected toxicities. Once the root of the higher than anticipated toxicities has been determined, the study team will confer with the FCCC DSMC and IRB to make a determination whether accrual can be resumed or the study will be terminated early. The chance of early termination with a true toxicity of 50% is 61%. The chance of study termination under the null of 20% true toxicity is 2.7% and is 83% if true toxicity is 50%.

As discussed earlier, no second line therapies have been prospectively evaluated in high grade neuroendocrine carcinomas and small retrospective studies have shown dismal results with chemotherapy [11-13]. Hence we decided to proceed without a definite stopping rule for futility, given minimal if any, harm associated with ineffective therapy to study participants.]

Correlative studies: Due to this limited sample size, all exploratory analyses of associations of biomarkers with outcomes and changes in marker levels pre- and during treatment will be largely descriptive in nature.

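### For hypophysitis, the Table 3 row and the 42-day rules require discontinuation without exception, while the Table 3 Note exempts endocrinopathies controlled on hormone replacement; no precedence is stated

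*Combined protocol and SAP*

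**What the plan says.** Five places in the protocol bear on a patient with persistent hypophysitis.

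- **Table 3, hypophysitis row, Grade 2-3.** Treatment is held, restart requires Grade 0-1, and the subject is discontinued if "Toxicity does not resolve to grade 0-1 within 6 weeks of last dose or inability to reduce corticosteroid to 10 mg or less"; the steroid criterion is a daily prednisone-equivalent dose, judged at 12 weeks. The row makes no exception for hormone replacement.
- **Table 3 Note.** "Permanently discontinue for persistent grade 2 or 3 adverse reactions (excluding endocrinopathies controlled with hormone", continuing "replacement therapy) that do not recover to Grade 0-1 within 6 weeks after last dose of Pembrolizumab".
- **Sections 7.1 and 6.0.** Section 7.1 states: "Patients requiring treatment to be held > 42 days for recovery from toxicity must discontinue protocol treatment". Section 6.0 sets the same 42-day limit for any treatment delay. Neither has an endocrine exception.
- **Section 6.4.3, hypophysitis.** For Grade 2 and for Grade 3-4 events: "Replacement of appropriate hormones may be required as the steroid dose is tapered".
- **Use in the analysis.** Section 4.6.2 bases the primary safety analysis on patients whose toxicity obliges them to stop under Section 7.0. Section 13.1 sets a review at 6 of the first 12 patients, and then: "If ever 8 of the 21 eligible patients have to discontinue study treatment due to treatment related adverse events", the study is suspended.

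**The concern.** The row and the Note use the same grades, the same target grade and the same 6 weeks after the last dose. They differ only in the exemption. Section 6.4.3 expects hormone replacement in hypophysitis, so a patient who is controlled on replacement and still Grade 2 or 3 at 6 weeks is a foreseeable case.

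For that patient the protocol gives two answers to whether discontinuation is required. Section 4.6.2 takes its definition from Section 7.0, and Section 13.1 counts patients who are obliged to discontinue. The same clinical course can therefore be counted or not counted in the primary safety variable and against the stopping boundaries, depending on which line a site applies.

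**Working it through.** **Step 1. The texts side by side, for a patient controlled on replacement and still Grade 2 or 3 six weeks after the last dose.**

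| Text | Trigger | Endocrine exemption | Discontinuation required? |
|---|---|---|---|
| Hypophysitis row | Not Grade 0-1 within 6 weeks of last dose | None | Yes |
| 42-day rules (6.0, 7.1) | Hold or delay over 42 days | None | Yes, once the hold passes 42 days |
| Table 3 Note | Not Grade 0-1 within 6 weeks of last dose | Controlled on hormone replacement | No |

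The 42-day rules run on the length of the hold. Counted from the last dose, they bind at 6 weeks. Counted from the first missed dose of a 21-day cycle, they bind at 21 + 42 = 63 days. Either way they reach a patient who stays above Grade 0-1, because the row offers no other restart route.

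The hypothyroidism row allows treatment to continue, and the Type 1 diabetes row has its own condition for resuming; neither conflicts with the Note. The Grade 3 hyperthyroidism row repeats the hypophysitis text, and Section 6.4.3 also foresees hormone replacement there, so it needs the same check.

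**Step 2. The plan's own stopping figures.** Inputs from Section 13.1: boundaries of 6 of 12 and 8 of 21, and true rates of 20% and 50%. The exact chance of reaching either boundary at rate p is

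P(X12 ≥ 6) + Σ(x = 0 to 5) P(X12 = x) · P(X9 ≥ 8 − x).

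- First boundary at 50%: P(X12 ≥ 6) = 0.6128. This reproduces the stated 61%.
- Either boundary at 20%: 0.0194 + 0.0309 = 0.0503.
- Either boundary at 50%: 0.6128 + 0.2974 = 0.9102.

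The stated overall figures of 2.7% and 83% do not follow from 8 of 21; they reproduce with 9 of 21 (0.0274 and 0.8326). That is a separate matter. The figures below use the boundaries as written, so their base is 5.0%, not 2.7%.

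**Step 3. Effect of a shift in the counted rate.** The documents give no hypophysitis rate, so the points added by the stricter reading are an assumption.

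| Points added to 20% | Expected extra patients in 21 | Chance of reaching either boundary |
|---|---|---|
| 0 | 0 | 0.0503 |
| 1 | 0.01 × 21 = 0.21 | 0.0640 |
| 2 | 0.02 × 21 = 0.42 | 0.0800 |
| 5 | 0.05 × 21 = 1.05 | 0.1428 |

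**Step 4. Effect of one patient.** One reclassified patient moves the observed rate by 1/21 = 4.8 points. It alters a stopping decision only when the count is one short of a boundary:

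- Exactly 5 of 12 at 20%: C(12,5) · 0.2^5 · 0.8^7 = 792 × 0.00032 × 0.2097 = 0.053.
- Exactly 7 of 21 at 20%: C(21,7) · 0.2^7 · 0.8^14 = 116280 × 0.0000128 × 0.04398 = 0.0655.
- At 30% the same two probabilities are 0.1585 and 0.1725.

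**The case against.** The strongest reply is that a note under a table normally qualifies the rows above it, so the exemption is an ordinary exception to the endocrine rows. That is a reasonable reading, but the protocol does not state it. It also leaves the row's restart condition and both 42-day rules without an exemption.

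The opposite reply is that the row, its restart condition and the 42-day rules all point to discontinuation, which leaves the Note as the outlier. On a literal reading this has force. But the Note's exemption then does nothing for hypophysitis, although it is written for endocrinopathies controlled on replacement. Both replies are tenable, and that is why the text needs reconciling.

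The practical objections stand. Few patients will meet all the conditions. Reaching a boundary starts a review rather than automatic termination, and a disputed hypophysitis case would be visible in that review.

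Three stronger readings are tempting, and the documents do not support them:

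- **That one patient is ordered both to stop permanently and to continue.** The Grade 2-3 row does not say permanently; that word is in the Note and the Grade 4 line. The Note lifts a requirement to stop and does not order continuation.
- **That the Type 1 diabetes row contradicts Section 7.1.** The row says "Resume Pembrolizumab when patients are clinically and metabolically stable" and Section 7.1 says "subjects may resume Pembrolizumab upon resolution of toxicity to Grade 0-1 or baseline". The latter is limited to subjects whose dose interval was increased for toxicity, so a specific row beside it is not a clear contradiction. What remains is that the resume text appears in the column of discontinuation criteria, which may be an effect of text conversion.
- **That the stopping rule is badly distorted.** A 10-point shift would give 29.4%, but it would need about 0.10 × 21 = 2.1 extra such patients, and nothing in the documents supports that.

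**Conclusion.** Table 3 is internally inconsistent for hypophysitis: the row and the Note apply the same 6-week test with and without an exemption, the 42-day rules side with the row, and no precedence is given. The conclusion rests on the wording alone and needs no assumed rate.

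The effect on the trial is probably small. Each affected patient changes the primary safety variable and the stopping count by one. Under an assumed 1 to 5 point rise on a 20% rate, with independent patients and the boundaries as written, the chance of reaching a boundary goes from 5.0% to 6.4%-14.3%; the lower end looks more realistic given how many conditions a patient must meet. The point should still be corrected, because the ambiguous rule also defines the primary safety variable.

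**What to change.** Reconcile the Grade 2-3 hypophysitis row, the Table 3 Note and the 42-day rules in Sections 6.0 and 7.1, so that a single rule says whether an endocrinopathy controlled on hormone replacement is subject to the 6-week and 42-day limits. Amending the row and the Note alone would leave the conflict with the 42-day rules. Check the hyperthyroidism row in the same pass. Which clinical rule applies is for the sponsor to decide.

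Then state in Sections 4.6.2 and 13.1 that the primary safety analysis and the stopping counts use the reconciled rule.

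As an editorial item only, check that the resume text in the Type 1 diabetes row is in the intended column.

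The cost is a wording correction in the next amendment, with no added patients, visits or tests.
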